6.2.2 Prohibited medication

Except for protocol allowed concomitant medication or any medication which may be required to treat adverse events, no medication other than study treatment will be allowed from the date the participant signs the inform consent until EOS.

Participants should not receive any antiperistaltic, antidiarrheal agents or stool softeners from Screening through Day 28. These agents include, but are not limited to, bismuth subsalicylate, atropine and diphenoxylate, loperamide, octreotide, opium tincture, cholestyramine, colestipol, colace, or lactulose. Participants should not consume yogurt, kefir or probiotics (e.g. *Saccharomyces boulardii*) up to Day 21 or initiation of nitazoxanide, whichever comes first. All medications, procedures and significant non-drug therapies (including physical therapy and blood transfusions) administered after the participant is enrolled into the study must be recorded on the appropriate Case Report Forms.

In addition, other than those administered per protocol, participants should not receive any antibacterial or anti-parasitic therapy with possible activity against *Cryptosporidium* up to Day 28 (see Section 6.2.3).

Warfarin or drugs that prolong the QTc interval are not permitted between Screening and Day 28 unless deemed necessary by the Investigator (participants on warfarin or drugs that prolong the QTc interval are not permitted to enter the study (see Section 5.2).

Vaccinations are not permitted between Day -14 and Day 28 but are permitted outside this window (including COVID-19 vaccinations).

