A second course of nitazoxanide and/or other antiparasitic drug(s) (e.g. paromomycin alone or in combination with azithromycin) may be considered for participants with severe diarrhea or treatment failure after nitazoxanide monotherapy at the discretion of the Investigator. The duration of treatment will depend upon the participant's response to therapy. Although controlled, large-scale trials are lacking, the use of combination therapy is supported by findings from small case series (Smith et al 1998). Paromomycin (500 mg three times daily for one week) is generally used as an alternative agent if nitazoxanide cannot be used. All antimicrobial therapy for cryptosporidiosis administered before Day 28 will be recorded in eCRF as a concomitant medication.

Participants will not receive nitazoxanide if:

- they did not shed oocysts at any time after Day 3 and
- they did not have diarrhea between Day 1 and Day 21 and
- there was no diagnosis of cryptosporidiosis in any of the participant's household contacts between Day 11 and Day 21

In participants with severe diarrheal illness, oral and/or intravenous hydration, and replacement of electrolytes as needed, is expected as part of the standard of care management of adverse events (dehydration and severe diarrhea). Fluid replacement therapy will be recorded as a concomitant medication in the eCRF.

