2.2 Analysis sets

For all analysis sets, participants will be analyzed according to the dose of ABO809 received (*C. parvum* oocysts, also referred to as "treatment").

The full analysis set (FAS) and safety analysis set (SAF) will be comprised of all participants who took one dose of ABO809 during the treatment period.

The Pharmacodynamic (PD) analysis set includes all participants with available parasitological and clinical data and with no protocol deviations with relevant impact on PD data. Fecal stool samples will also be assessed for other enteric pathogens which may cause diarrheal illness. Any participant with a positive test for these other enteric pathogens will be excluded.

The protocol deviation codes are summarised in Appendix Section 5.6.

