Nitazoxanide will be administered at 500 mg by mouth every 12 hours with food for 3 days as per the U.S. Prescribing Information, under the clinical conditions outlined below. All participants who receive ABO809 and develop an infection (i.e. oocyst shedding after Day 3 or sooner if associated with symptoms of diarrheal illness), will receive nitazoxanide on Day 21 or as soon as results of EIA analysis (and confirmed by DFA if positive) of Day 17 sample becomes available whether or not they develop clinical symptoms. There are conditions under which participants may receive nitazoxanide earlier: (i) participants with diarrhea persisting until Day 10 will start nitazoxanide on Day 10, (ii) participants with severe diarrheal illness (≥ Grade 3 as per Toxicity Grading Scale for Healthy Adult and Adolescent Volunteers Enrolled in Preventive Vaccine Clinical Trials (2007)) may receive nitazoxanide unless deemed contraindicated by the Investigator irrespective of timing. Whenever nitazoxanide treatment is administered to participants experiencing clinical symptoms, participants may be domiciled at the discretion of the Investigator until free of clinical symptoms for ≥24 hours. A second course of nitazoxanide may be considered for participants with severe diarrhea or treatment failure following first course of nitazoxanide at the discretion of the Investigator. The duration of treatment will depend upon the participant's response to therapy.

Participants will not receive nitazoxanide if:

- they did not shed oocysts at any time after Day 3 and
- they did not have diarrhea between Day 1 and Day 21 and
- there was no diagnosis of cryptosporidiosis in any of the participant's household contacts between Day 11 and Day 21

The summary of the following characteristics may be provided by ABO809 treatment group and cohort number:

- Tabulation of number of participants who required nitazoxanide on Day 21 with confirmation that all 3 doses of nitazoxanide are taken on consecutive days
- Tabulation of number of participants who required nitazoxanide earlier or if the participant requires a second course of nitazoxanide
- Tabulation of number of participants who had evidence of infection or clinical symptoms after last dose of nitazoxanide

Other rescue medications (other antiparasitic drug(s) e.g. paromomycin alone or in combination with azithromycin) will be captured under rescue medication category.

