2.4 Analysis supporting primary objective(s) (PD analysis set)

2.4.1 Primary endpoint(s)

The primary endpoint is *Cryptosporidium* infection up to Day 10 (inclusive). This is defined as detection of oocysts

- in at least one fecal sample at \geq 72 hours after ABO809 administration
- or sooner than 72 hours if associated with symptoms suggestive of diarrheal illness, in at least one fecal sample after ABO809 administration.

Fecal stool samples will be assessed for *Cryptosporidium* infection using a commercially available diagnostic EIA test and confirmed by DFA test if the EIA is positive. Tests will be performed at a CLIA certified laboratory. Samples that test negative for *Cryptosporidium* by EIA will be reported as negative for *Cryptosporidium* without confirmation by DFA.

To overcome stool-to-stool and day-to-day oocyst shedding variability, up to 3 consecutive stool specimens, produced about 3-4 hours apart and on the same day will be tested. If at least one of the stool samples is *Cryptosporidium* positive, the participant will be considered infected. Otherwise, the participant will not be considered infected.

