2.5 Analysis supporting secondary objectives

The secondary objectives of this study are to (1) evaluate the incidence and characteristics of diarrheal illness (PD analysis set), (2) to evaluate the time to onset and resolution of *Cryptosporidium* infection (PD analysis set), and (3) to assess the safety and tolerability of ABO809 (Safety analysis set).

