5.1.3.3 Other imputations

N/A

5.2 **Prohibited medications**

Table 5-4 Table of prohibited medication with respective ATC codes

Prohibited medication	ATC code	ATC name
Antiperistaltic, antidiarrheal agents or	A02BX22	Bismuth subsalicylate
stool softeners	A03BA01	Atropine
	A07DA01	Diphenoxylate
	A07DA03	Loperamide
	H01CB02	Octreotide
	A07DA02	Opium tincture
	C10AC01	Cholestyramine
	C10AC02	Colestipol
	A06AA02	Docusate sodium
	A06AD11	Lactulose
Antithrombotic agents and other	B01AA03	Warfarin
agents prolonging QTc interval		
Antibacterial agents and other anti-parasitic therapies	A07AA06	Paromomycin alone or in combination with azithromycin
Yogurt, kefir, probiotics	N/A	N/A
vaccinations	N/A	N/A

AEs coding/grading 5.3

Grading will be assessed using the U.S. Food and Drug Administration's (FDA) "Toxicity Grading Scale for Healthy Adult and Adolescent Volunteers Enrolled in Preventive Vaccine Clinical Trials (2007)". For AE reporting based on laboratory values, local laboratory normal ranges may be used at the discretion of the Investigator, and if so, must be used consistently throughout the study. These may differ from the normal ranges given in the FDA grading scale. In case of such discrepancies, the Investigator will take into consideration the FDA recommendations as to the magnitude of deviations from normal provided in the FDA grading scale.

For AEs that are not contained in the "Toxicity Grading Scale for Healthy Adult and Adolescent Volunteers Enrolled in Preventive Vaccine Clinical Trials (2007)" the following categorization will be used:

- Mild: usually transient in nature and generally not interfering with normal activities
- Moderate: sufficiently discomforting to interfere with normal activities
- Severe: prevents normal activities

Stools will be graded according to this Stool Grading System by the Investigator. Grades 1 and 2 are considered normal stool and Grades 3-5 are considered diarrheal stool.

Table 5-5 Stool Grading System

Clinical Stool Classification	Stool Grade	Stool Description
Normal stool	1	Formed stool which does not take the shape of the container
Normal stool	2	Soft stool which does not easily take the shape of the container
Diarrheal stool	3	Thick liquid stool which does take the shape of the container
Diarrheal stool	4	Opaque watery stool
Diarrheal stool	5	Rice water stool, clear watery stool

Levine et al 1988, Sack et al 1998, Tribble et al 2009

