5.6 Rule of exclusion criteria of analysis sets

Table 5-6 Protocol deviations leading to exclusion

	9	
Analysis Set	Criteria that cause subjects to be excluded	
SAF	Not treated with study treatment;	
PD	Not having informed consent; Not treated with study medication;	
	Not meeting entry criteria;	
	No evaluable, parasitological and clinical data;	
	Use of prohibited medication or vaccination during the study;	

6 Reference

Clopper, C. J. and Pearson, E. S. (1934), "The Use of Confidence or Fiducial Limits Illustrated in the Case of the Binomial," *Biometrika*, 26, 404-413.

Collett, D. (1994), Modeling Survival Data in Medical Research, London: Chapman & Hall.

ICH E9(R1) Harmonized Guideline: addendum on estimands and sensitivity analysis in clinical trials to the guideline on statistical principles for clinical trials. Final version on 20 November 2019.

Toxicity Grading Scale for Healthy Adult and Adolescent Volunteers Enrolled in Preventive Vaccine Clinical Trials (2007). Guidance for Industry. U.S. Food and Drug Administration (Internet) Available from: (Accessed 09 July 2021).

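### SAP Table 5-4 lists paromomycin as prohibited without the protocol's exemption for per-protocol use, so Table 5-6 read literally drops participants given it as permitted rescue from the PD set

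*SAP*

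**What the plan says.** **Treatment named as rescue.** Protocol 6.2.3 leaves further treatment to the investigator's judgment. Besides a repeat of nitazoxanide, it has this wording: "e.g. paromomycin alone or in combination with azithromycin) may be considered for participants with severe diarrhea or treatment failure after nitazoxanide monotherapy". It also mentions paromomycin as the usual alternative when nitazoxanide cannot be used. SAP 2.3.4 classifies the same treatment in the same way: "paromomycin alone or in combination with azithromycin) will be captured under rescue medication category".

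**Treatment banned, with an exemption.** Protocol 6.2.2 states the ban, up to Day 28, as follows: "other than those administered per protocol, participants should not receive any antibacterial or anti-parasitic therapy". Rescue given under 6.2.3 is therefore outside the ban.

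**Treatment banned, without an exemption.** SAP Table 5-4 (section 5.2) has a row for antibacterial and antiparasitic agents. Its only entry is "Paromomycin alone or in combination with azithromycin", under the ATC code for paromomycin. The row says nothing about use as rescue.

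**Consequence for the analysis set.** SAP Table 5-6 (section 5.6) gives this as a ground for exclusion from the PD set: "Use of prohibited medication or vaccination during the study". It has no time window and no exception for rescue.

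**Where the PD set is used.** The heading of SAP 2.4 reads "Analysis supporting primary objective(s) (PD analysis set". SAP 2.5 assigns the same set to the incidence and characteristics of diarrheal illness and to time to onset and resolution of infection; only safety uses the safety set.

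**Handling of rescue elsewhere.** SAP 2.2 limits the PD set to participants "with no protocol deviations with relevant impact on PD data". SAP 2.4.3 sets negative infection results after rescue to missing in the time profiles. SAP 2.5.3 right-censors day-count, duration and stool-weight variables at rescue, and censors Kaplan-Meier times there.

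**The concern.** One drug is both a permitted rescue and a listed ground for exclusion. A programmer who matches concomitant medications to the code in Table 5-4 and then applies Table 5-6 would remove per-protocol rescue users from the PD set. Rescue antiparasitics given before Day 28 are recorded as concomitant medication, so that match would pick them up.

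Such an exclusion depends on what happened after dosing. Paromomycin would mainly follow severe diarrhea or failure of nitazoxanide, often after the Day 10 infection status is already known to be positive. Dropping those participants takes established infections out of the numerator and the denominator of the primary proportion, and takes any later positive results out of the by-visit tables that run to the end of the study. SAP 2.4.3 was written to keep such positives.

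No sensitivity analysis is planned for the primary or secondary endpoints. The full analysis set is defined but not assigned to these analyses, so nothing visible in the plan would show the effect. SAP section 4 declares no change to the protocol's analyses, so the lost exemption looks like an oversight.

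**Working it through.** **1. Does the literal rule reach these participants?**

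| Step | Source | Result for a participant given paromomycin under Protocol 6.2.3 |
|---|---|---|
| Is the drug banned? | Protocol 6.2.2 | No, because it is given per protocol |
| Is the drug banned? | SAP Table 5-4 | Yes, no exception |
| How is it classed? | SAP 2.3.4 | Rescue medication |
| Excluded from the PD set? | SAP 2.2 | No, because there is no protocol deviation |
| Excluded from the PD set? | SAP Table 5-6 with Table 5-4 | Yes |
| How are later data handled? | SAP 2.4.3, 2.5.3 | Negatives set to missing, or censored; participant kept |

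Tables 5-4 and 5-6 together say exclude. Everything else says retain.

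**2. The plan's own precision figures.** Protocol 12.8.1 assumes a true incidence of 90% and uses the 1-sided 80% exact interval. Take the largest x with P(X ≥ x | n, 0.90) ≥ 0.80. The lower limit is the 20th percentile of Beta(x, n − x + 1).

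| n | x | P(X ≥ x) | Lower limit | Stated |
|---|---|---|---|---|
| 20 | 17 | 0.867 | 74.1% | 74% |
| 30 | 26 | 0.825 | 78.6% | 78% |
| 60 | 52 | 0.858 | 81.6% | 81% |

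All three reproduce when truncated to whole percent, so the same formula is used below.

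**3. Size of the effect.** Assume 27 of 30 infected, which is the protocol's 90%, and let k infected participants be dropped for paromomycin use. The estimate is (27 − k)/(30 − k). The 1-sided 80% limit uses the 20th percentile of the Beta distribution. The SAP's 2-sided 80% Clopper-Pearson interval (SAP 2.4.2 and 5.5.1) uses the 10th.

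| k | Infected/n | Estimate | 1-sided 80% lower limit | 2-sided 80% lower limit |
|---|---|---|---|---|
| 0 | 27/30 | 90.0% | 82.4% | 79.1% |
| 1 | 26/29 | 89.7% | 81.8% | 78.4% |
| 2 | 25/28 | 89.3% | 81.2% | 77.7% |
| 3 | 24/27 | 88.9% | 80.5% | 76.9% |

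SAP 2.1 also reports by cohort. With 9 of 10 infected:

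| k | Infected/n | Estimate | 1-sided 80% lower limit | 2-sided 80% lower limit |
|---|---|---|---|---|
| 0 | 9/10 | 90.0% | 72.9% | 66.3% |
| 1 | 8/9 | 88.9% | 70.2% | 63.2% |
| 2 | 7/8 | 87.5% | 67.0% | 59.4% |

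**4. How large could k be?** The documents give no rate of paromomycin use. They give nitazoxanide response as 96% (Protocol 6.2.3) and as 80-93% (Protocol 4.1), so non-response is 4% to 20%. Among 27 treated infected participants that is 27 × 0.04 = 1.1 to 27 × 0.20 = 5.4 failures. This counts failures, not paromomycin users: a second nitazoxanide course is also available and is not listed in Table 5-4. If five failures all received paromomycin, the result would be 22/25 = 88.0%, with lower limits of 79.0% (1-sided) and 75.2% (2-sided).

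**5. Time to resolution and duration.** Under SAP 2.5.3 a participant still shedding at the first nitazoxanide dose is censored there. Shedding after a failed course never enters as observed time. Excluding that participant loses only the at-risk time before first rescue.

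**The case against.** The strongest reply is that the plan, read as a whole, already retains these participants. Table 5-6 is headed as a list of protocol deviations, SAP 2.2 excludes only for deviations that matter to PD data, and Protocol 6.2.2 says that per-protocol therapy is not a deviation. SAP 2.3.4 and 2.5.3 treat the drug as rescue. On that reading the tables merely lack a carve-out. This stands as an argument for what the authors meant. It does not remove the conflict, because the tables are what a programmer would apply, and they say the opposite.

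The reply also limits what a reader might infer:

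- *Participants whose infection persists after nitazoxanide are deleted.* Not supported. The trigger is paromomycin use, which is discretionary.
- *The longest shedders disappear from time to resolution and duration.* Not supported. Censoring at first rescue already cuts off their later follow-up.
- *Shedding after nitazoxanide would be reported as zero.* Not supported. The rescue-medication summaries in SAP 2.3.4 and the adverse event of special interest for persistent shedding use the safety set.
- *The bias must be downward.* Not guaranteed. Rescue for severe diarrhea does not require confirmed infection, and dropping one uninfected user would give 27/29 = 93.1%.
- *Dose decisions are affected.* Not shown. Protocol 6.5.1 uses its own definition of evaluable data, not the PD set.

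It is also fair that the primary analysis is descriptive and that the shift at 30 participants is small. The sparse coding of the row may be only illustrative: the QTc row likewise codes one drug.

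**Conclusion.** The concern holds as an unresolved contradiction in the analysis-set rules, not as a demonstrated bias. Applied literally, Tables 5-4 and 5-6 make a permitted, outcome-related rescue a reason to leave the PD set, against SAP 2.2, 2.4.3 and 2.5.3 and Protocol 6.2.2.

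In the illustration each infected participant lost at 30 costs about 0.3 to 0.4 points on the estimate and 0.6 to 0.8 points on the lower limit, 1-sided or 2-sided. In a cohort of 10 the cost is about 1.1 to 1.4 points on the estimate and 2.7 to 3.8 on the limit. These figures rest on three assumptions: 90% observed infection, users who are all infected, and a number of users that the documents do not give and that may be zero.

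The point is worth settling despite its size, because otherwise the choice between exclusion and retention could be made after it is known who was rescued and what their results were.

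**What to change.** Reconcile Protocol 6.2.2 and 6.2.3, SAP 2.3.4, Table 5-4 and Table 5-6 on this one point:

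- Carry the protocol's exemption for therapy given per protocol into Table 5-4, so that the antibacterial and antiparasitic row covers use outside the protocol only.
- State in Table 5-6 that protocol-permitted rescue is not a PD-set exclusion, and that antibacterial or antiparasitic use outside the protocol remains one.
- State that paromomycin, alone or with azithromycin, given as rescue under Protocol 6.2.3 is handled by the rules in SAP 2.4.3 and 2.5.3.
- Decide from the recorded reason for use, not from the ATC code alone, since the code cannot separate rescue from other use.

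The cost is a short SAP edit before database lock, plus one check in the derivation of the PD set. No new data are needed, and the choice, dose and timing of rescue treatment are untouched.

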5.4 Laboratory parameters derivations

Grading will be assessed using the U.S. Food and Drug Administration's (FDA) "Toxicity Grading Scale for Healthy Adult and Adolescent Volunteers Enrolled in Preventive Vaccine Clinical Trials (2007)", see Section 2.6.3.

5.5 Statistical models

5.5.1 Analysis supporting primary objective(s)

The primary analysis of *Cryptosporidium* infection at ≥72 hours post-administration (or sooner if associated with symptoms suggestive of diarrheal illness) up to Day 10 (inclusive is detailed in Section 2.4.1.

SAS procedure FREQ with EXACT statement for one-way tables will be used to estimate the proportion of responders (binary outcome = 1 or "Yes"), along with the associated 80% 2-sided Clopper-Pearson CI (Clopper and Pearson 1934).

5.5.2 Analysis supporting secondary objective(s)

Kaplan-Meier estimates

An estimate of the survival function in each treatment group will be constructed using Kaplan-Meier (product-limit) method as implemented in PROC LIFETEST with METHOD=KM option. The PROC LIFETEST statement will use the option CONFTYPE=LOGLOG.

Median survival for each treatment group will be obtained along with 90% confidence intervals calculated from PROC LIFETEST output. Kaplan-Meier estimates of the survivor function with 90% confidence intervals at specific time points will be summarized. The standard error of the Kaplan-Meier estimate will be calculated using Greenwood's formula (Collett 1994).

5.6 Rule of exclusion criteria of analysis sets

Table 5-6 Protocol deviations leading to exclusion

	9	
Analysis Set	Criteria that cause subjects to be excluded	
SAF	Not treated with study treatment;	
PD	Not having informed consent; Not treated with study medication;	
	Not meeting entry criteria;	
	No evaluable, parasitological and clinical data;	
	Use of prohibited medication or vaccination during the study;	

6 Reference

Clopper, C. J. and Pearson, E. S. (1934), "The Use of Confidence or Fiducial Limits Illustrated in the Case of the Binomial," *Biometrika*, 26, 404-413.

Collett, D. (1994), Modeling Survival Data in Medical Research, London: Chapman & Hall.

ICH E9(R1) Harmonized Guideline: addendum on estimands and sensitivity analysis in clinical trials to the guideline on statistical principles for clinical trials. Final version on 20 November 2019.

Toxicity Grading Scale for Healthy Adult and Adolescent Volunteers Enrolled in Preventive Vaccine Clinical Trials (2007). Guidance for Industry. U.S. Food and Drug Administration (Internet) Available from: (Accessed 09 July 2021).

